#### 4.7.1.3 Pharmacokinetic Parameters

The following PK parameters will be determined for each subject:

- Urine
  - Cumulative amount excreted in urine over 24 h ( $A_{e0-24}$ )
  - Total fraction of dose excreted in urine (Total Fe)
  - Renal clearance (ranitidine) ( $CL_R$ )
- Plasma
  - AUC from time 0 extrapolated to infinity ( $AUC_{0-\text{inf}}$ )
  - AUC from time 0 to the sampling time corresponding to the last quantifiable concentration ( $C_{\text{last}}$ ) ( $AUC_{0-t}$ )
  - Maximum concentration (observed peak drug concentration) ( $C_{\text{max}}$ )
  - Time at which  $C_{\text{max}}$  occurs ( $T_{\text{max}}$ )
  - Elimination rate constant ( $K_{\text{el}}$ )

- Terminal half-life ( $t_{1/2}$ )

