Urine samples will be collected using separate collection containers over 24 h. Collection times will occur at 0 (pre-dose), 3, 6, 9, 12, 15, and 24 h on study dosing days. Subjects will be instructed to void their bladder at each collection time and total weight of the sample will be recorded. If a subject must void their bladder at an unscheduled time (highly discouraged), the unscheduled voids will be collected, and total weight of the unscheduled voiding will be recorded. The unscheduled voiding sample will be treated, analytically analyzed, and reported as part of scheduled sample collection for determining cumulative amounts of NDMA, ranitidine, and DMA excreted over 24 h. Plasma samples for NDMA, DMA, and ranitidine analysis will be collected at 0 (pre-dose), 0.5, 1, 1.5, 2, 3, 4, 5, 6, 9, 11, 14, and 24 h post-dose on study dosing days.

The study will be conducted at one center in the United States (Spaulding Clinical Research unit in West Bend, Wisconsin). Each treatment group will attempt to include equal representation of male and female subjects.

Table 1: Study Treatments

Treatment	Drug
A	Ranitidine (300 mg) + low nitrite/NDMA meals
B	Placebo + low nitrite/NDMA meals
C	Ranitidine (300 mg) + high nitrite/NDMA meals
D	Placebo + high nitrite/NDMA meals

Table 2: Study Design

Day -2	Day -1	Day 1	Day 2	Day 3	Day 4	Day 5	Day 6	Day 7	Day 8
Check-in	Washout	Period 1	Washout	Period 2	Washout	Period 3	Washout	Period 4	Check-out

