4.2 Exploratory Endpoints

The exploratory endpoints of this study are:

1. AUC from time 0 extrapolated to infinity (AUC_{0-inf}) of plasma ranitidine, NDMA and DMA
2. Cumulative ranitidine and DMA amount excreted in urine over 24 h after ranitidine administration

5. Analysis Populations

The PK population will include all subjects who receive study drug and have at least one on-treatment sample. The safety population will include all subjects who receive at least 1 dose of any of the study drugs. The analysis population will include all subjects in the PK population with sufficient data to calculate PK parameters from at least two study periods of the same meal

type (i.e., low nitrite/NDMA or high nitrite/NDMA). Treatment in all analysis populations will be assigned based upon the treatment which the subjects actually received.

6. Data Screening and Acceptance

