Cumulative amounts of DMA and ranitidine will be log-transformed. A mixed-effect analysis of variance (ANOVA) approach will be used for comparing arithmetic means (for NDMA) and geometric means (for DMA and ranitidine) looking at the effects of treatment, period, and sequence. For NDMA, testing will be one-sided at a 0.05 significance level, and a significant increase will be concluded if the lower bound of the one-sided 95% interval for the arithmetic mean difference excludes 0. For DMA and ranitidine, testing will be one-sided at a 0.05 significance level, and a significant increase will be concluded if the lower bound of the one-sided 95% interval for the geometric mean ratio excludes 1. The results will be transformed back to the original scale by exponentiation to provide treatment geometric means.

Normality assumption of the ANOVA will be verified using the Shapiro-Wilke test for normality and homogeneity of variances will be verified using Levene's test. If either assumption is not valid, a Wilcoxon signed-rank test will be used for the comparison rather than an ANOVA.

Individual and mean time course plots of NDMA, DMA, and ranitidine excreted over 24-hr will be evaluated for each treatment. All urine PK parameters will be summarized using descriptive statistics (number of subjects, mean, SD, coefficient of variation [CV], median, minimum, and maximum) for NDMA, DMA, and ranitidine. Individual time course plots will use actual sampling times. Treatment mean plots will use planned sampling times.

All calculations and the hypothesis testing will be done using R software.

Total fraction of the ranitidine dose excreted in urine ($Fe_{0-24, \text{ranitidine}}$) will be determined for Treatments A and C based on the cumulative amount of ranitidine excreted in urine over 24-h ($Ae_{0-24, \text{ranitidine}}$) divided by 300 mg. This will be calculated for each individual, summarized using descriptive statistics (number of subjects, mean, SD, CV, median, minimum, and maximum), and visualized graphically using box-and-whisker plots.

Renal clearance of ranitidine will be determined (only for Treatments A and C) by calculating the rate of excretion as the difference between the later and earlier compound level divided by the difference in times points (i.e., $[\text{amount}_{t_2} - \text{amount}_{t_1}] / [t_2 - t_1]$). The log-transform of the renal

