excretion will be plotted against the midpoint of each time stop. This will be fit to a linear regression using least-squares fitting and the slope and intercept will be used to determine the overall renal clearance. This will be calculated for each individual and summarized using descriptive statistics (number of subjects, mean, SD, CI, median, minimum, and maximum). All calculations will be done using R software.

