7.3.2 Plasma Pharmacokinetics

The following PK parameters will be determined for NDMA, DMA, and ranitidine (only Treatments A and C) for each subject based on all available concentration-time points:

- **AUC from time 0 to the sampling time corresponding to the last quantifiable concentration (C_{last}) (AUC_{0-t})**

AUC_{0-t} will be calculated according to the linear trapezoidal rule from 0 h to the last quantifiable concentration after drug administration.

- **AUC from time 0 extrapolated to infinity (AUC_{0-inf})**

AUC_{0-t} will be extrapolated to infinity from the AUC from time 0 to the sampling time corresponding to the last quantifiable concentration plus the last quantifiable concentration divided by K_{el} , as follows:

$$AUC_{0-inf} = AUC_{0-t} + C_{last}/K_{el}$$

- **Maximum concentration (observed peak drug concentration) (C_{max})**

C_{max} will be read directly from the observed concentrations.

- **Time at which C_{max} occurs (T_{max})**

T_{max} will be read directly from the observed concentrations as the blood sampling time corresponding to C_{max} . The earlier time will be reported in cases where the same C_{max} value is observed for a subject at multiple timepoints

- **Terminal half-life ($t_{1/2}$)**

The terminal half-life will then be calculated using the elimination rate constant as:

$$t_{1/2} = \ln(2)/K_{el}$$

- **K_{el}**

The terminal elimination rate constant, which will be determined from the terminal slope of the log-concentration curve using linear regression

The PK parameters will be analyzed using noncompartmental methods based on actual sampling times. Serum concentrations below the limits of quantification will be set to zero for the purpose of this analysis (see Section 6). AUC_{0-inf} , $t_{1/2}$, and K_{el} for each analyte and subject will only be

included if the subject has 3 or more concentration values on the terminal portion of the pharmacokinetic curve and with an adjusted coefficient of determination (R^2) greater than 0.80.

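### SAP 7.3.1 derives ranitidine renal clearance from log excretion rate against time with no plasma term, so the slope and intercept do not identify it

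*SAP*

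**What the plan says.** Protocol 4.7.1.3 and the synopsis list renal clearance of ranitidine as a urine PK parameter without saying how it is calculated. The only method is in SAP 7.3.1, in three steps:

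1. Excretion rate per urine interval: "Renal clearance of ranitidine will be determined (only for Treatments A and C) by calculating the rate of excretion", taken as the change in urinary amount divided by the change in time.
2. The log of that rate is plotted against the interval midpoint and a least-squares line is fitted.
3. From that line, "the slope and intercept will be used to determine the overall renal clearance".

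On use of the result, the SAP says: "This will be calculated for each individual and summarized using descriptive statistics". No test is attached. SAP 4.2 does not list CLR as an endpoint; its urine item is "Cumulative ranitidine and DMA amount excreted in urine over 24 h after ranitidine administration".

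Plasma ranitidine is handled separately. SAP 7.3.2 says: "The following PK parameters will be determined for NDMA, DMA, and ranitidine (only Treatments A and C) for each subject". It defines AUC0-t and AUC0-inf but does not link either to renal clearance.

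**The concern.** Renal clearance relates the rate of urinary excretion to the plasma concentration. A plot of log excretion rate against time contains no plasma information; it is a way to estimate an elimination rate constant. The plan describes a specific calculation, names its result renal clearance, and gives no step that turns the fitted line into one.

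The analyst must then either invent a plasma step, which different analysts could do differently, or report a quantity that is not a clearance. The reach is narrow, but CLR is a protocol-listed parameter that will be reported for each subject under two treatments.

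**Working it through.** The documents give no figure for CLR, so there is nothing of the plan's own to reproduce. The check has three parts.

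**Inputs from the documents**
- Dose D: 300 mg, oral.
- Urine collections: 0, 3, 6, 9, 12, 15 and 24 h (SAP 3.1), giving midpoints 1.5, 4.5, 7.5, 10.5, 13.5 and 19.5 h.
- Plasma samples: 0, 0.5, 1, 1.5, 2, 3, 4, 5, 6, 9, 11, 14 and 24 h (SAP 3.1).

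**Assumed inputs** (the documents give no ranitidine kinetics): one-compartment oral model, bioavailability F 0.5, absorption rate ka 1.2/h, no noise, no quantification limit. The elimination rate k, volume V and clearances are set in each case.

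**1. Units and algebra**

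The regression uses mg and h only. Its slope is in 1/h and exp(intercept) is in mg/h. No combination of the two, even with the 300 mg dose, gives L/h. This does not depend on any kinetic model.

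Under the assumed model:
- Excretion rate = CLR × C(t), with C(t) = F·D·ka / [V(ka − k)] × (e^(−kt) − e^(−ka·t)).
- After absorption, ln(rate) = ln{(CLR/V)·F·D·ka/(ka − k)} − k·t.

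The late slope is −k. CLR enters the intercept only as CLR/V, mixed with F and ka.

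**2. The SAP's regression on simulated subjects**

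Amount per interval = CLR × exact plasma AUC over that interval; rate = amount / interval length; ln(rate) regressed on midpoint, all six intervals.

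| Case | V (L) | k (1/h) | True CLR (L/h) | Slope | Intercept |
|---|---|---|---|---|---|
| (a) k and renal fraction 0.7 fixed | 30 | 0.25 | 5.25 | -0.2225 | 3.208 |
| | 60 | 0.25 | 10.5 | -0.2225 | 3.208 |
| | 120 | 0.25 | 21 | -0.2225 | 3.208 |
| (b) CLR fixed, non-renal clearance 4.5 L/h, k = 15/V | 30 | 0.50 | 10.5 | -0.440 | 3.990 |
| | 60 | 0.25 | 10.5 | -0.2225 | 3.208 |
| | 120 | 0.125 | 10.5 | -0.108 | 2.465 |
| (c) V and non-renal clearance 4.5 L/h fixed, k = (CLR + 4.5)/60 | 60 | 0.1625 | 5.25 | -0.1425 | 2.481 |
| | 60 | 0.25 | 10.5 | -0.2225 | 3.208 |
| | 60 | 0.425 | 21 | -0.3761 | 3.963 |

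In (a), a four-fold range of CLR gives one fit. In (b), one CLR gives three fits. In (c), the fit does move with CLR, so the defect is non-identification and not insensitivity in every setting.

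A second parameter set (CLR/V 0.15/h, k 0.25/h, ka 1.0/h, F 0.5, V 50 to 200 L) gives the same picture: true CLR of 7.5, 15, 22.5 and 30 L/h all give slope -0.2175 and intercept 3.0366. With the first interval dropped, all four give -0.2361 and 3.2957.

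**3. Ae0-24 / AUC0-24 on the same subjects**

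AUC0-24 is the linear trapezoid on the planned plasma times. In case (a), Ae0-24 is 104.67 mg for all three subjects:
- V 30 L: 104.67 / 20.33 = 5.15 L/h (true 5.25)
- V 60 L: 104.67 / 10.165 = 10.30 L/h (true 10.5)
- V 120 L: 104.67 / 5.083 = 20.59 L/h (true 21)

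The error is -1.9% each time. Over ka of 0.6, 1.2 and 2.4/h crossed with k of 0.15, 0.25 and 0.40/h, it runs from -2.52% to +0.03%. In the second parameter set the estimates are 7.34, 14.69, 22.03 and 29.37 L/h.

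**The case against.** The strongest reply is that the text is incomplete and not wrong. It does not say that slope and intercept are the only inputs, and AUC0-inf is derived for the same subjects and treatments. Under the assumed model, exp(intercept)/|slope| approximates total urinary recovery, and dividing that by AUC0-inf gives a clearance. For case (a), exp(3.208)/0.2225 is about 111.2 mg. AUC0-inf = F·D/(k·V) = 150/(0.25·V), which is 20, 10 and 5 mg·h/L. The results are 5.56, 11.12 and 22.23 L/h, about 6% high; across (a) to (c) the error is about +4% to +17%. So a cruder route through the regression exists, and an unwritten plasma step cannot be excluded. But that step is not in the SAP, which does write out formulas for AUC0-inf, half-life and fraction excreted. Even with it, the result is less accurate than the direct ratio.

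Other points that stand:
- The slope estimates k only in the terminal phase. With all six intervals it is -0.2225 against k of 0.25, about 11% low in size.
- Case (a) has identical urine profiles by construction. It demonstrates the unit argument and does not estimate the error expected in this trial.
- The quoted accuracy of the ratio covers plasma AUC only. SAP 7.3.1 multiplies urine weight by 1.01 although volume is to come from a specific gravity of 1.01. If the weight should be divided, Ae0-24, and hence CLR, is high by 1.01² = 1.0201, about 2%. This affects the regression's rates equally.
- AUC0-24 is one workable denominator; a stated formula using another AUC would also close the gap.

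**Conclusion.** The point holds. As written, the SAP's procedure cannot return a renal clearance, because nothing in it carries a volume. That conclusion rests on units alone. The numerical illustrations rest on assumed one-compartment oral kinetics without noise or a quantification limit, and show how far the fit and the true value can separate: a four-fold range of CLR on one fitted line.

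The consequence is minor. No hypothesis test or listed endpoint uses CLR, the primary NDMA comparison is untouched, and correct values can be calculated from samples the plan already collects.

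**What to change.** In SAP 7.3.1, replace the regression with CLR = Ae0-24 / AUC0-24 of plasma ranitidine, per subject, for Treatments A and C.

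In SAP 7.3.2, define AUC0-24, since only AUC0-t and AUC0-inf are defined there: linear trapezoid over the 0 to 24 h samples, actual sampling times, values below quantification taken as zero as SAP 6.1 already provides. Numerator and denominator then cover the same interval.

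State that CLR is not calculated for a period with a missed void. SAP 6.1 does not impute uncollected urine, so Ae0-24, and with it CLR, would be too low.

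The cost is a few lines of SAP text and R code; no new samples or assays are needed.

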7.3.2 Plasma Pharmacokinetics

The following PK parameters will be determined for NDMA, DMA, and ranitidine (only Treatments A and C) for each subject based on all available concentration-time points:

- **AUC from time 0 to the sampling time corresponding to the last quantifiable concentration (C_{last}) (AUC_{0-t})**

AUC_{0-t} will be calculated according to the linear trapezoidal rule from 0 h to the last quantifiable concentration after drug administration.

- **AUC from time 0 extrapolated to infinity (AUC_{0-inf})**

AUC_{0-t} will be extrapolated to infinity from the AUC from time 0 to the sampling time corresponding to the last quantifiable concentration plus the last quantifiable concentration divided by K_{el} , as follows:

$$AUC_{0-inf} = AUC_{0-t} + C_{last}/K_{el}$$

- **Maximum concentration (observed peak drug concentration) (C_{max})**

C_{max} will be read directly from the observed concentrations.

- **Time at which C_{max} occurs (T_{max})**

T_{max} will be read directly from the observed concentrations as the blood sampling time corresponding to C_{max} . The earlier time will be reported in cases where the same C_{max} value is observed for a subject at multiple timepoints

- **Terminal half-life ($t_{1/2}$)**

The terminal half-life will then be calculated using the elimination rate constant as:

$$t_{1/2} = \ln(2)/K_{el}$$

- **K_{el}**

The terminal elimination rate constant, which will be determined from the terminal slope of the log-concentration curve using linear regression

The PK parameters will be analyzed using noncompartmental methods based on actual sampling times. Serum concentrations below the limits of quantification will be set to zero for the purpose of this analysis (see Section 6). AUC_{0-inf} , $t_{1/2}$, and K_{el} for each analyte and subject will only be

included if the subject has 3 or more concentration values on the terminal portion of the pharmacokinetic curve and with an adjusted coefficient of determination (R^2) greater than 0.80.

AUC_{0-inf} and C_{max} will be compared with either low nitrite/NDMA meals (comparison between Treatments A and B, respectively) or high nitrite/NDMA meals (comparison between Treatments C and D, respectively) using a paired t-test. Normality assumption will be verified using the Shapiro-Wilke test for normality. If the assumption is not valid, the data will be log-transformed, and then tested for normality. Homogeneity of variances will be verified using Lavene's test. If the data in its original or transformed form does not meet the t-test assumptions, a Wilcoxon signed-rank test will be used for the comparison rather than a paired t-test.

These PK parameters will be summarized using descriptive statistics (number of subjects, mean [arithmetic for NDMA; geometric for DMA and ranitidine], SD, coefficient of variation [CV], median, minimum, and maximum) for NDMA, DMA, and ranitidine.

All parameters will be calculated using R software. Mean and individual concentration-time profiles will be presented in graphs.

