2.0	General (Rationale)	NDMA analyses will be based on arithmetic means instead of geometric means. Blinded review of the bioanalytical data revealed that a large number of urine and plasma samples for NDMA were below the lower limit of quantification (LLOQ). For multiple subjects, all samples from 1 or more study periods were below the LLOQ. As zero values cannot be log-transformed for geometric mean analyses, these periods would have been removed from analysis. Furthermore, as analyses are paired, these subjects would have been removed from analyses. Utilizing arithmetic mean will allow data from all subjects and all periods to be used in the planned analysis. Ranitidine and DMA analyses will remain the same (i.e. utilizing geometric means).
	7.3.1	Analysis of urine concentrations Analysis of NDMA urine 24-hr excretion will be performed using arithmetic means instead of geometric means.
	7.3.2	Plasma pharmacokinetics Descriptive statistics for plasma PK parameters of NDMA will be calculated using arithmetic means.

1. Introduction

This document outlines the proposed statistical methods for data analysis of data collected from Protocol ‘SCR-010 Clinical study to investigate the urinary excretion of N-nitrosodimethylamine (NDMA) after ranitidine administration’.

2. Objectives

The following analysis plan provides the framework for the summarization of the data from this study. The analysis plan may change due to unforeseen circumstances but will be finalized prior to database lock. Any changes made after the database lock will be documented and justified in the clinical study report.

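### SAP 7.3.2 lets the 0 h pre-dose sample supply plasma Cmax and Tmax, and a single DMA Tmax of 0 h makes the planned geometric mean zero or undefined

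*SAP*

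**What the plan says.** SAP 7.3.2 determines the plasma parameters for NDMA, DMA and ranitidine "for each subject based on all available concentration-time points". SAP 3.1 gives the schedule: "Plasma samples for NDMA, DMA, and ranitidine analysis will be collected at 0 (pre-dose), 0.5, 1, 1.5, 2, 3, 4, 5, 6, 9, 11", then 14 and 24 h, which makes 13 samples per period. Protocol 4.7.1.1 lists the same times.

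Cmax is read from the observed concentrations. Tmax "will be read directly from the observed concentrations as the blood sampling time corresponding to" Cmax, with a tie rule: "The earlier time will be reported in cases where the same" maximum occurs more than once. A post-dose phrase does appear in the section, but only in the definition of AUC0-t: "from 0 h to the last quantifiable concentration after drug administration". Neither document excludes the pre-dose sample from Cmax or Tmax, and neither corrects for baseline.

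Cmax is then tested, A against B and C against D. Ranitidine is determined only in A and C, so these tests concern NDMA and DMA. The parameters are summarised with, among other statistics, a "mean [arithmetic for NDMA; geometric for DMA and ranitidine". Values below the quantification limit are set to zero (SAP 6.1 and 7.3.2).

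**The concern.** For a drug that is absent before dosing, including the 0 h sample in the search for a maximum does no harm. NDMA and DMA are different, because the plan itself treats both as possibly present without ranitidine. SAP 7.3.1 compares them between the two placebo treatments to look for a meal effect. SAP 3.2 cites 11-380 ng of urinary NDMA per 24 h on placebo. High nitrite/NDMA meals are also served on the washout days before treatments C and D. A quantifiable pre-dose value is therefore possible.

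Two things can follow. First, a value drawn before the dose can become that treatment's Cmax and enter the A-B or C-D test. Second, Tmax can be 0 h, and a geometric mean cannot accommodate a zero. The SAP change log recognises this problem for NDMA amounts ("As zero values cannot be log-transformed for geometric mean analyses, these periods would have been removed from analysis") and moves NDMA to arithmetic means, but it leaves the DMA summaries geometric.

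**Working it through.** The plan states no figure on this point, so there is none to reproduce. The check applies the written rules literally: Cmax is the maximum of 13 samples, Tmax is the earliest time of that maximum, values below the limit are 0, and the geometric mean is exp(mean(log x)).

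**1. Does the geometric mean fail?** Take 17 subjects with Tmax 3 h and one with 0 h (illustrative values). Since log(0) is minus infinity, the geometric mean is 0; the arithmetic mean is 17 × 3 / 18 = 2.83 h. SAP 7.3.2 uses actual sampling times, so a pre-dose draw could also carry a slightly negative time. With -0.1 h in place of 0 the result is undefined. If the one value were 0.5 h, the earliest planned post-dose time, the geometric mean would be exp[(17 ln 3 + ln 0.5)/18] = 2.72 h.

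**2. How likely is at least one DMA Tmax of 0 h?** The documents give no plasma DMA profile, pre-dose level or within-profile variability, so every figure here is conditional on an assumption.
- Flat profile with 13 exchangeable samples: 1/13 = 7.7% per subject-period. For 18 subjects, 1 - (12/13)^18 = 76% per treatment; for 14 subjects, 67%.
- Pre-dose level 10% lower: 30% (CV 15%) to 53% (CV 30%) among 18. Pre-dose level 20% lower: 5% to 28%.
- Post-dose rise of 25% over 1 to 4 h: 3% (CV 10%) to 32% (CV 20%). Two-fold rise: 0.1% or less.
- For a per-subject probability simply set at 0.5%, 1%, 2% or 5%, the chance among 18 is 8.6%, 16.5%, 30.5% or 60.3%.

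**3. How much does Cmax move?** For DMA, including the 0 h sample raises Cmax by about 0% to 1.1% across the flat and lowered pre-dose profiles, and by under 1% in the runs with CV 10% to 20%.

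For NDMA, suppose each sample is quantifiable with probability q and is otherwise 0. The expected number of subjects per treatment with only the pre-dose sample quantifiable is 18 × q × (1 - q)^12, and the share of non-zero Cmax values this represents is q(1 - q)^12 / [1 - (1 - q)^13]:

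| q | Subjects per treatment | Share of non-zero Cmax |
|---|---|---|
| 0.03 | 0.37 | 6.4% |
| 0.05 | 0.49 | 5.5% |
| 0.10 | 0.51 | 3.8% |
| 0.20 | 0.25 | 1.5% |

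Over the same range, simulated mean NDMA Cmax rises by 7.1% down to 3.2%. The larger percentages apply to a mean made up largely of zeros: at q = 0.03, 0.97^13 = 67% of profiles have no quantifiable sample.

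**4. Periods with every NDMA sample below the limit.** The change log reports such periods for multiple subjects. Here Cmax = 0 and, by the tie rule, Tmax = 0 h. The NDMA mean is arithmetic and stays defined, but it takes in artificial zeros. Restricting the rule to post-dose samples without further provision would turn these into an equally artificial 0.5 h.

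**The case against.** The SAP labels Cmax as the observed peak drug concentration, and usual PK practice would read that as post-dose. This is a fair pointer, but the instruction to use all available points goes the other way, and a program written to the text would search all 13 samples.

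The geometric-mean sentence could be read as covering only AUC0-inf and Cmax. However, SAP 7.3.2 lists Tmax among its PK parameters, protocol 4.9.6.2 names Tmax among those summarised with a mean, and the protocol synopsis asks for a geometric mean for all parameters.

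Three further objections stand. The planned summary already includes median, minimum and maximum, which remain valid with a Tmax of 0 h, and Tmax is never tested. The 0 h sample follows a 12 h fast and breakfast starts within two minutes of dosing, so exchangeability of the 13 samples is a strong assumption. And in a flat background profile none of the samples reflects the treatment, so dropping one of 13 does not turn Cmax into a treatment effect; separating background from effect is what the placebo period is for.

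A reader might also infer that pre-dose maxima arise mainly on placebo and so pull the ranitidine-placebo difference toward zero. That has not been shown. The simulations assume no drug effect, and then both periods are inflated alike and the expected paired difference is unchanged. No calculation here includes a drug effect or a test result.

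**Conclusion.** The defect is in the text: as written, the pre-dose sample is eligible for Cmax and Tmax. The firm part is the DMA Tmax summary, which fails as soon as one subject peaks at 0 h. The 76% should not be read as the expected frequency. It is the top of a range that starts near 0, and the documents do not locate the trial within that range. The Cmax part is real but small under every assumption tried, with no demonstrated direction of bias in A-B or C-D.

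The importance is minor. Cmax and Tmax are not listed endpoints; the listed plasma endpoint, AUC0-inf, is exploratory. The 24-hour urinary NDMA endpoint does not use these rules.

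**What to change.** In SAP 7.3.2:
- Define Cmax as the highest concentration observed after dosing (0.5 to 24 h), and Tmax as the time of that value.
- State that the 0 h sample is kept for the AUC and the listings but is not eligible for Cmax or Tmax.
- Set Tmax to missing when all post-dose values are below the quantification limit (Cmax = 0).
- Summarise Tmax for all analytes by median, minimum and maximum only, with no geometric mean.

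This costs a few sentences and a minor program edit, with no new data. The one small downside is that Cmax is taken over 12 samples rather than 13.

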6.1 Handling of Missing and Incomplete Data

The following imputation of missing values will be done:

- PK measurements (urine or plasma) below the quantification limits will be considered equal to zero for all analyses.
- Missing PK data (e.g., skipped plasma sample collected or uncollected urine voids) will not be imputed.

7. General Statistical Considerations

All data will be presented in data listings. Data from subjects excluded from an analysis population will be presented in the data listings, but not included in the calculation of summary statistics.

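### Read literally, the SAP's BLQ-as-zero and earliest-tie rules place NDMA Tmax at the pre-dose sample in any plasma period with no quantifiable value, which can distort a descriptive table

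*SAP*

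**What the plan says.** Several rules in the SAP act together.

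- **BLQ values.** SAP 6.1: "PK measurements (urine or plasma) below the quantification limits will be considered equal to zero for all analyses". SAP 7.3.2 repeats the rule for the noncompartmental plasma analysis.
- **Points used.** SAP 7.3.2 determines the plasma parameters "for each subject based on all available concentration-time points". It does not restrict Cmax or Tmax to post-dose samples.
- **Sampling times.** SAP 3.1: "Plasma samples for NDMA, DMA, and ranitidine analysis will be collected at 0 (pre-dose), 0.5, 1, 1.5, 2, 3", then 4, 5, 6, 9, 11, 14 and 24 h. That is 13 samples, the first taken before dosing.
- **Tmax.** SAP 7.3.2 says that Tmax "will be read directly from the observed concentrations as the blood sampling time corresponding to" Cmax. For ties: "The earlier time will be reported in cases where the same" Cmax value is seen at several timepoints.
- **Evaluability.** The requirement in SAP 7.3.2 for at least three terminal values and an adjusted R² above 0.80 applies to AUC0-inf, t1/2 and Kel. It does not mention Cmax or Tmax.
- **Reporting.** SAP 7.3.2 summarises the plasma parameters by n, mean (arithmetic for NDMA), SD, CV, median, minimum and maximum.

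The version 2.0 entry in the SAP change log says that many urine and plasma NDMA samples were below the LLOQ, and adds: "For multiple subjects, all samples from 1 or more study periods were below the LLOQ". It gives this as the reason for moving the NDMA analyses to arithmetic means, so that every subject and period can be used.

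**The concern.** Each rule is ordinary when taken alone. Setting BLQ to zero is a common convention, and so is taking the first of several tied maxima. Together they return a number where there is nothing to measure. If no concentration in a period is quantifiable, all values are zero, all times tie, and the tie rule picks the first sample. The result is a time of peak that precedes the dose. It comes from rules the SAP states, and code that takes the first maximum will produce it without a warning.

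Version 2.0 was written because many NDMA values were BLQ, and it revised the NDMA descriptive statistics in 7.3.2, but Tmax was not addressed. The summary table for NDMA Tmax would then mix real peak times with placeholder times from periods without a detectable peak. Within the table, the two could not be told apart. Plasma NDMA after ranitidine compared with placebo is a stated exploratory objective, so the table is likely to be read.

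**Working it through.** The plan gives no figure for this point, so there is none to reproduce. The check applies the rules as written.

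**Step 1: an all-BLQ period.** Inputs: 13 planned plasma times (SAP 3.1) and BLQ = 0 (SAP 6.1 and 7.3.2).

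- Concentrations: 0 at each of the 13 times.
- Cmax = maximum of 13 zeros = 0.
- Times at which the concentration equals Cmax: all 13.
- Earlier-time rule: Tmax = 0 h, the pre-dose sample.

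Two variants lead to the same problem. With actual sampling times, as SAP 7.3.2 requires, the pre-dose time may be slightly below zero. If the pre-dose sample is missing, Tmax becomes the first available time, for example 0.5 h.

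**Step 2: a period with one quantifiable value.** If only the 3 h sample is quantifiable, Cmax is that value and Tmax = 3 h. A partly BLQ profile like this one does not show the artefact.

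**Step 3: effect on the summary.** Assumptions, not figures from the documents: 18 periods per treatment (the planned enrolment, no dropouts); Tmax = 2 h in every quantifiable period; k of the 18 periods all BLQ.

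- Mean = 2 × (18 − k) / 18.
- Median = average of the 9th and 10th ordered values.
- Minimum = 0 h once k is at least 1.

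| k (assumed) | Mean | Median | Minimum |
|---|---|---|---|
| 0 | 2.00 h | 2 h | 2 h |
| 1 | 2 × 17/18 = 1.89 h | 2 h | 0 h |
| 6 | 2 × 12/18 = 1.33 h | 2 h | 0 h |
| 9 | 2 × 9/18 = 1.00 h | 1 h | 0 h |
| 10 | 2 × 8/18 = 0.89 h | 0 h | 0 h |

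The mean falls in proportion to the share of all-BLQ periods. The median holds at 2 h up to k = 8, is 1 h at k = 9, and is 0 h from k = 10. If quantifiable periods peak at 3 h instead, k = 6 gives a mean of 2.0 h and a median of 3 h, and k = 9 gives 1.5 h for both.

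**Step 4: after the fix.** When all-BLQ periods are left out, the mean, median and minimum are each 2 h in this example for any k below 18, over n = 18 − k periods.

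**The case against.** The strongest objection is about consequence. The primary endpoint is urinary NDMA. The exploratory endpoints are plasma AUC0-inf and urinary ranitidine and DMA. SAP 7.3.2 compares only AUC0-inf and Cmax between treatments. Tmax appears in descriptive tables alone, so no test, interval or conclusion planned in the SAP depends on it. This stands, and it limits the point to a minor one.

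A reader might infer three stronger things, and the documents support none of them.

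- **That the SAP records all-BLQ plasma periods.** The change log speaks of urine and plasma samples together and does not say in which fluid the whole-period findings arose. Its argument about log-transformation and pairing fits the urinary primary analysis at least as well. All-BLQ plasma periods are plausible, but they are not documented or counted.
- **That placebo would show the earlier Tmax.** The review behind version 2.0 was blinded and gives no counts by treatment. The background points both ways: an earlier volunteer study reported a rise of about 400-fold with ranitidine, while FDA laboratory tests found no NDMA formed in typical stomach conditions. With equal shares of all-BLQ periods, the artefact shifts both summaries by the same proportion.
- **That the Tmax summaries become useless.** In the illustration the median is untouched up to 8 of 18 periods. The SAP also lists all data and plots individual profiles, so a flat line with Cmax = 0 can be recognised. This helps a careful reader but does not correct the tabulated mean or minimum.

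There is also some room in the wording. The SAP reads Cmax and Tmax from observed concentrations, and a programmer could decide that an imputed zero is not observed and return a missing value. The explicit zero rule for all analyses makes this the weaker reading. That two programmers could differ is itself a reason to settle the text.

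**Conclusion.** The point holds as a minor defect in a descriptive output. Read literally, the SAP gives a pre-dose Tmax to any plasma NDMA period in which every value is BLQ, and no other rule in the SAP prevents it.

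The size cannot be known from the documents, because the number of such periods, the fluid concerned and the treatment are not given. Under the stated assumptions the mean falls in direct proportion to the share of all-BLQ periods, the minimum becomes 0 h with the first one, and the median fails only when about half of the periods are affected. If the share differs between treatments, in either direction, the tabulated Tmax would differ through detection frequency alone, even where true timing is the same. The primary urinary analysis and the tests of AUC0-inf and Cmax are unaffected.

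**What to change.** Add one sentence to SAP 7.3.2: when all concentrations of an analyte in a period are BLQ, Tmax is reported as 'not determined' and left out of the Tmax summary, and the number of such periods is given for each treatment. Keep Cmax = 0 for these periods under the existing BLQ rule, so that the Cmax comparison is unchanged.

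The cost is a smaller n for Tmax, which may differ between treatments. The count of excluded periods should therefore stand in the same table: it shows how often nothing was detected, which the pre-dose Tmax would have hidden.
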